12.5	Movement Specific Reinvestment Scale.....	29

1 Study Synopsis

Title	A pilot cluster randomised controlled trial, of an implicit learning approach (ILA) versus standard care, on recovery of mobility following stroke.
Protocol Short Title/Acronym	Implicit Learning in Stroke Study (IMPS)
Protocol Version Number and Date	V2 24/09/2018
Study Phase	Pilot (with embedded feasibility)
Study Hypothesis	None
Study Duration	24 months
Methodology	Cluster (Stroke Unit) randomised controlled pilot trial, with nested qualitative exploration of participant and therapist views.
Sponsor Name	Royal Bournemouth and Christchurch Hospitals NHS Foundation Trust and University of Southampton
Chief Investigator	[name]
REC Number	[to be added]
Medical condition under investigation	Stroke
Primary Objective	To establish the feasibility of delivering an ILA during acute stroke rehabilitation (fidelity), and to test the integrity of the study protocol (pilot).
Secondary Objective(s)	To generate data to inform the design of a Phase III trial – including: 
 • Identification of training requirements of clinical teams delivering ILA • Identification of most appropriate outcome measure • Estimation of expected rates of recruitment and retention • Estimation of effect size to enable future sample size calculation • Therapist and patient perceptions of the approach
Number of Clusters	6-8
Number of Participants	60
End Point	3 months post stroke
Main Inclusion Criteria	Clinical diagnosis of stroke; presenting with hemiplegia Within 14 days of stroke onset Medically stable Able to 
 • tolerate daily therapy for a minimum of 30 minutes per session • sit for more than 5 seconds without support • understand and follow 1 stage commands
Primary Outcome Measure	Change in modified Rivermead Mobility Index score at 4 weeks.
Statistical Methodology and Analysis	Within group change scores for all outcome measures with 95% confidence interval

2 Abbreviations

AI	Adverse Incident
HASU	Hyperacute Stroke Unit
ILA	Implicit Learning Approach
FM-LL	Fugl Meyer Assessment – Lower Limb Section
MDT	Multidisciplinary Team
mRMI	Modified Rivermead Mobility Index
MSRS	Movement Specific Reinvestment Scale
SU	Stroke Unit
SwePASS	Modified (Swedish) Postural Adjustment in Stroke Scale

3 Background and Rationale

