4.5 Recruitment of Individual Participants

4.5.1 Eligibility Criteria for Participants

Inclusion criteria

- Clinical diagnosis of stroke; presenting with hemiplegia
- Within 14 days of stroke onset
- Medically stable
- Able to
 - tolerate daily therapy for a minimum of 30 minutes per session
 - sit for more than 5 seconds without support
 - understand and follow 1 stage commands

Exclusion criteria

- Previous stroke with residual impairments
- Other neurological diagnosis (e.g. PD, MS)
- Clinically relevant pre-morbid disability levels

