4.12 Measures

Measures will be performed and recorded by the stroke research practitioner(s), or designated clinician, at each site. As the research practitioner will not be blind to the intervention arm, all measures will be video recorded, and later scored by a blinded second assessor. Frequent measures are required to understand *rate* of change. Outcome measures have been selected with consideration of international recommendations for measurement of sensorimotor recovery in stroke [12].

At baseline:

- Movement Specific Reinvestment Scale (Self-Report Questionnaire) (MSRS)

At baseline, week 2, week 4, week 6 post enrolment (or up to the point of discharge):

- Fugl Meyer – motor leg sub section
- Modified Postural Adjustment in Stroke Scale (SwePASS)
- Modified Rivermead Mobility Index (mRMI)
- Able to sit for 1 minute unsupported?
- Able to transfer from bed to chair independently?
- Able to walk 10m independently?

At point of discharge

- Discharge destination and care requirements immediately on discharge (number of care visits per day multiplied by the number of carers required)
- Fugl Meyer – motor leg sub section
- Modified Postural Adjustment in Stroke Scale (SwePASS)
- Modified Rivermead Mobility Index (mRMI)
- Able to sit for 1 minute unsupported?
- Able to transfer from bed to chair independently?
- Able to walk 10m independently?
- Movement Specific Reinvestment Scale (MSRS)

At 3 months post enrolment:

- Fugl Meyer – motor leg sub section
- Modified Postural Adjustment in Stroke Scale (SwePASS)
- Modified Rivermead Mobility Index (mRMI)
- Able to sit for 1 minute unsupported?
- Able to transfer from bed to chair independently?
- Able to walk 10m independently?
- Modified Rankin Scale (mRS)
- EQ-5D
- Movement Specific Reinvestment Scale (MSRS)

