4.16 Analysis

Data will be stored and managed using SPSS. Statistical support will be provided by the University of Southampton. Double data entry will be used for paper-based assessments.

The unit of analysis is the individual patient. As this is a pilot study, analysis will primarily be descriptive. Descriptive methods will be used to estimate feasibility of factors relating to the protocol, such as recruitment (proportion of eligible people who consent to the study) and retention (completion of outcome measures at 4 weeks).

Fidelity of the interventions will be established by comparing the number and type of coaching statements delivered to each group. We will describe the mean number of coaching statements per person (and the breakdown of these statements as externally- or internally-focussed) in each group. While we expect large differences, we will not formally test the difference as the study is not designed to do so; we will instead provide an estimate of the difference with corresponding 95% confidence interval. Differences in outcome and potential effect size for the Fugl Meyer, SwePASS and mRMI will be calculated using confidence interval estimation.

5 Process Evaluation

To enable us to understand patient and therapist perceptions and experiences of the ILA, will we be inviting a sub-set of participants to take part in a qualitative evaluation of the ILA.

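### The primary outcome and the only named retention measure are set at 4 weeks, but the visible text does not say how patients discharged before week 4 are handled

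*Combined protocol and SAP*

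**What the plan says.** - Section 1 (Study Synopsis) gives the primary outcome as "Change in modified Rivermead Mobility Index score at 4 weeks".
- Section 4.16 (Analysis) gives one example of a retention measure: "retention (completion of outcome measures at 4 weeks". It comes after a phrase that leaves the list open, so other retention measures are not excluded, but none is named.
- Section 4.12 (Measures) schedules the repeated assessments as follows: "At baseline, week 2, week 4, week 6 post enrolment (or up to the point of discharge". It then lists a separate assessment at discharge, with the same six motor measures including mRMI, and another at 3 months with no inpatient limit.
- Section 4.9 (Duration of Treatment) ties trial treatment to the inpatient stay and accepts that discharge dates will vary.
- For the analysis, the synopsis plans "Within group change scores for all outcome measures with 95% confidence interval". Section 4.16 adds: "Differences in outcome and potential effect size for the Fugl Meyer, SwePASS and mRMI will be calculated using confidence interval estimation". Neither says at which visit the between-arm difference is taken.
- The synopsis lists among its secondary objectives "Estimation of expected rates of recruitment and retention" and "Estimation of effect size to enable future sample size calculation", both to inform a Phase III trial.

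**The concern.** The outcome and the retention measure are fixed at week 4, while the schedule that supplies them may end sooner. In the visible text, no week-4 assessment is scheduled after discharge, and no rule says whether the discharge score stands in for week 4.

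Retention and effect size are two of the quantities the pilot exists to deliver. If planned discharge is not kept apart from loss, a patient who goes home on schedule and is assessed at 3 months is recorded in the 4-week figure in the same way as one who disappears. A 4-week mRMI change based only on those still in hospital describes that group, not everyone recruited. Whether a week-4 score exists may also be related to the score itself: section 3 names ability to transfer as a criterion for early discharge, and transfers are an item of the mRMI (section 12.2).

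**Working it through.** **Timing.** Eligibility is "Within 14 days of stroke onset" (section 4.5.1), and week 4 is counted from enrolment (section 4.12). An inpatient week-4 value therefore needs a stay to day 28 after enrolment, which is up to 14 + 28 = day 42 after stroke.

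**Two readings of the same text for a patient who leaves before day 28.**
- Literal: there is no scheduled week-4 measure, so no 4-week mRMI change, and the retention definition is not met.
- Substitution: the discharge mRMI is used. The patient is counted, but the follow-up time is the day of discharge, anywhere up to day 28.

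**The plan's own figure.** Section 4.13 asks for 7-10 participants per cluster from 60 participants in 6-8 clusters: 60/8 = 7.5 and 60/6 = 10. This agrees, with the lower end rounded down. The total of 60 cannot be re-derived, because the recruitment and retention rates behind it are not stated.

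**Effect on recorded retention under the literal reading.** Each early discharge lowers 4-week completion by 1/60 = 1.7 points overall, or 1/30 = 3.3 points in an arm of 30 (equal arms assumed). The share discharged before week 4 is not in the documents, so it is an assumption. With nobody truly lost:

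| Assumed share discharged before week 4 | Recorded retention (Wilson 95% CI) |
|---|---|
| 10% | 54/60 = 90% (79.9 to 95.3) |
| 30% | 42/60 = 70% (57.5 to 80.1) |
| 50% | 30/60 = 50% (37.7 to 62.3) |
| 70% | 18/60 = 30% (19.9 to 42.5) |

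**Illustrative threshold.** Suppose retention without this effect were k/60. The Wilson lower limit is [p + z²/2n − z√(p(1−p)/n + z²/4n²)] / (1 + z²/n), with p = k/60, n = 60 and z = 1.96. The smallest number m of otherwise retained early discharges that brings (k − m)/60 below that limit is:

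| Assumed k/60 | Lower limit | m | (k − m)/60 |
|---|---|---|---|
| 57/60 = 95% | 86.3% | 6 | 51/60 = 85.0% |
| 54/60 = 90% | 79.9% | 7 | 47/60 = 78.3% |
| 51/60 = 85% | 73.9% | 7 | 44/60 = 73.3% |
| 48/60 = 80% | 68.2% | 8 | 40/60 = 66.7% |

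Exact (Clopper-Pearson) limits give the same m. Clustering is ignored; allowing for it would raise the threshold.

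**Precision of the within-arm change.** The 95% CI half-width in SD units is t(0.975, n−1)/√n. It is 0.37 for n = 30, 0.42 for n = 24 and 0.46 for n = 21, corresponding to assumed early discharge of 0%, 20% and 30%. This shows lost precision only and says nothing about selection.

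**The case against.** The text never calls discharged patients non-completers. The limit at discharge in section 4.12 is followed by a discharge assessment with the same six measures, so it is reasonable to think that assessment closes the inpatient series and may be meant to count. The trial flowchart (section 4.6) and the CONSORT diagram (Appendix 1) are not shown and could hold the rule. The synopsis end point is 3 months, mRMI is scheduled then, and the open list in section 4.16 leaves room for 3-month retention. The trial has no hypothesis and a mainly descriptive analysis, so no test depends on the week-4 figure. Section 3 counts assisted transfer as meeting the discharge criterion, so early discharge need not mean a high mRMI score. The 6 to 8 threshold rests on assumed retention levels, and nothing shows that so many early discharges will occur.

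All of this stands, and it limits the point to handling that is not stated in the visible text. It does not remove the point. If the discharge score is meant to count, the resulting change is not a 4-week change, and that needs to be written down. The open list permits a 3-month retention figure but does not plan one.

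A reader might infer more: that the data for these patients are lost, that the fastest recoverers are removed, that the comparison between arms is biased, or that Phase III would be wrongly sized. The documents do not support these inferences. Discharge and 3-month scores are scheduled, and without length of stay the direction of any selection, its size and any difference between arms are unknown.

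**Conclusion.** The concern holds as a gap between the 4-week definitions and the assessment schedule. For a group of patients the plan itself expects, the visible text leaves both the primary outcome and the only named retention measure undefined. On either reading, the retention and effect-size figures carried into Phase III are harder to interpret.

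The actual size is unknown, because no length of stay is given. The figure of 6 to 8 in 60 (10% to 13%) shows only that a modest number would be enough to matter. It assumes underlying retention of 80% to 95% and independent patients. The conclusion also assumes that the figures not shown contain no rule. The gap is worth closing because the remedy is cheap.

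**What to change.** 1. Report week-4 status by arm in four categories: assessed, discharged before week 4, missed while an inpatient, and withdrawn or died. Do not count planned discharge as loss. Report retention at 3 months beside 4-week completion.
2. State in one sentence whether a discharge mRMI may count as the week-4 value; if it may, report the actual day. Label the 4-week change as applying to patients assessed at week 4. Beside it, report the 3-month mRMI change and the between-arm difference, each with a 95% CI, as the estimate scheduled for all patients.
3. As a separate and minor point, use one clock for the 3-month visit. The synopsis counts from stroke and section 4.12 from enrolment, which can differ by up to 14 days.

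The cost is wording and one table, from data already scheduled and with no new visits. There are two downsides. The 3-month estimate is later and includes a period of varying length after trial treatment ends at discharge (section 4.9). The change also labels the selection at week 4 without removing it. A week-4 visit after discharge would need extra resources and is not part of this recommendation.

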4.13 Proposed Sample Size

Our sample size calculation is based on estimated rates of recruitment and retention. We are aiming to recruit 60 participants in total, across the 6-8 clusters. Each cluster will therefore be required to recruit 7-10 participants.

4.14 Criteria for Premature Withdrawal

If there is a significant deterioration in a participants clinical signs (for example, if they have a further neurological event), then they will be withdrawn from the study. Reasons for withdrawal will be recorded.

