4.5.3.4 Process if a participant loses capacity during the study

[figure not shown]
Although unlikely, a participant who gave informed consent at the point of recruitment, may lose capacity during the course of the research. It is likely that any loss of capacity at this stage reflects medical instability - such as a further stroke, or an infection.

The study will adhere to the principles, as laid out and defined in the Mental Capacity Act (2005). At the time of the person consenting to the trial, they have expressed a wish to participate. Therefore, the person will remain in the study, as long as it is appropriate clinically, and there is no observable or communicated evidence that they do not wish to continue.

If the individual is communicating that they do not wish to continue in the trial, or are demonstrating an unwillingness to participate in any of the trial interventions (e.g. assessments, video recording, or therapy treatment sessions), then they will be withdrawn

The most likely cause of loss of capacity is a further stroke, or another medical event. In these circumstances, then (irrespective of capacity) the person will not be clinically appropriate to remain in the trial, and will be withdrawn.

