4.9 Duration of Treatment

Patients will be recruited as soon as eligible, and up to 14 days of stroke onset. Trial interventions will be delivered for the duration of each participant's inpatient stay, as deemed appropriate by the treating team. This approach is pragmatic and will ensure that the intervention can be fitted into the current care pathway, but accepting that discharge will be at different times for different patients.

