4.10 Training for Intervention Sites

For sites randomised to the intervention arm, all physiotherapists, occupational therapists and therapy assistants will be trained in the ILA. Training is anticipated to last no more than 3 hours. Additional training sessions will be offered if new members join the team during the recruitment phase. A manual including written, photographic and video resources will demonstrate how to adapt standard care interventions to the ILA. Therapists will be able to refer to the manual throughout their involvement in the study.

Whilst the wider multidisciplinary team (e.g. nurses, doctors, other AHP's) will not specifically be asked to change their approach with patients, those at intervention sites will be invited to attend a short education session to raise their awareness of the trial, and will be provided with written information about the study, and the concepts under investigation. As these professions wouldn't typically be analysing movement or giving specific instructions/feedback, this level of engagement is deemed appropriate and realistic.

The therapy team will be encouraged to give the MDT (particularly nurses) specific guidance about how to instruct an individual patient during movement (as part of a manual handling care plan, and in line with the ILA approach). These awareness raising sessions will support the MDT to understand and follow through these instructions.

As part of the training, clinical staff will be reminded of the options to withdraw participants from the study, should there be concerns about the impact the ILA has on their recovery (see 7.1.1).

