7.1 Assessment of Safety

7.1.1 Expected ILA Adverse Events

Although unlikely, there is a possibility that the ILA is perceived as less personal/motivating for patients, and this may be associated with a reduced willingness to participate in therapy. We will monitor adherence with rehabilitation across all sites. Non-compliance will be considered an AE if (i) a patient is declining to participate in rehabilitation sessions over a period of 5 days and (ii) the clinical team are unable to account for this in any other way. This will be addressed on an individual basis through discussion with the patient and the clinical team. If indicated, they will be withdrawn from the study.

If the treating team have any concerns about using the ILA with an individual patient, for example, should they feel that a patient is not responding /recovering as expected, they should discuss this with the Chief Investigator. If indicated, the participant will be withdrawn from the study, and their rehabilitation will revert to standard care. This decision will be taken on an individual basis, following discussion with the clinical team, Chief Investigator and (if appropriate) the participant. Withdrawal due to unanticipated/unexplained lack of progress in rehabilitation will be considered an AE.

It is important to note that, whilst therapists at the intervention sites are encouraged to adhere as much as possible to the ILA guidance, this is a pragmatic trial, and they can use their own clinical judgement during each individual treatment session. This is monitored as part of the feasibility aspect of this trial.

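### Section 7.1.1 lets poorly progressing ILA patients be withdrawn from the study, with no control counterpart and no readable plan to keep measuring them, so the between-arm estimates can drift towards ILA

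*Combined protocol and SAP*

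**What the plan says.** Three parts of the combined protocol and SAP remove participants from the study for clinical reasons.

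- **Section 7.1.1, poor progress.** The trigger is the treating team's concern about using the ILA, for example in a patient "not responding /recovering as expected". After a case-by-case discussion with the Chief Investigator: "If indicated, the participant will be withdrawn from the study, and their rehabilitation will revert to standard care". Section 4.10 builds this into intervention-site training: "clinical staff will be reminded of the options to withdraw participants from the study, should there be concerns about the impact the ILA has". The same section 7.1.1 also allows withdrawal for unexplained refusal of rehabilitation over 5 days; adherence is monitored at every site.
- **Section 4.14, deterioration.** A marked clinical decline leads to withdrawal: "for example, if they have a further neurological event), then they will be withdrawn from the study". Reasons are recorded.
- **Section 4.5.3.4, loss of capacity after a further stroke or other medical event.** "irrespective of capacity) the person will not be clinically appropriate to remain in the trial, and will be withdrawn".

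Section 4.9 gives trial treatment during the "inpatient stay, as deemed appropriate by the treating team". Section 4.12 schedules the mobility measures "At baseline, week 2, week 4, week 6 post enrolment (or up to the point of discharge", and again at discharge and at 3 months. Section 4.16 states: "Differences in outcome and potential effect size for the Fugl Meyer, SwePASS and mRMI will be calculated using confidence interval estimation". It defines retention by completion of outcome measures at 4 weeks. The synopsis names mRMI change at 4 weeks as the primary outcome, and an effect size for a future sample size calculation as a secondary objective.

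**The concern.** Stopping a treatment and stopping observation are different events, and the withdrawal wording treats them as one. Under 7.1.1 the reason for leaving is perceived poor recovery, which is close to what the primary outcome measures. The decision is made by people who know the allocation. The trigger is use of the ILA, so the rule can operate in one arm only.

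If those patients' later scores are not collected, the ILA arm keeps its better responders while the control arm keeps everyone. The between-arm estimates for mRMI, Fugl Meyer and SwePASS are then too favourable to ILA, and the synopsis intends an effect size from this pilot to inform Phase III.

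A feasibility result is blurred as well. Abandoning the ILA says something about the intervention; a missed assessment says something about follow-up. Withdrawal from the study merges the two in the 4-week retention figure.

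**Working it through.** **The plan's own figure.** Section 4.13 gives 60 participants over 6-8 clusters: 60/8 = 7.5 and 60/6 = 10, which agrees with the stated 7-10 per cluster. No withdrawal rate, SD, target difference or intracluster correlation (ICC) is given.

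**What happens to later outcomes.** Sections 4.12, 4.14, 4.16 and 7.1.1 contain no provision for outcomes after withdrawal, and 4.16 names no analysis set. The only data rule is in 4.5.3.3: for someone who regains capacity and opts out, data already collected are kept. It does not cover later outcomes. The flowchart (4.6) and CONSORT diagram (Appendix 1) are not readable, so they could hold something more.

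**Size of the shift.** Assumptions not in the documents:
- equal arms of 30;
- k ILA patients withdrawn under 7.1.1, all before week 4;
- their 4-week mRMI change, had it been measured, d points below that of the other ILA patients;
- no matching loss in control.

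The mRMI has 8 items scored 0-5 (Appendix 12.2), so its range is 0-40. If the retained ILA mean is m, the full-arm mean is ((30 - k)m + k(m - d))/30 = m - kd/30. The shift towards ILA is therefore kd/30.

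| k | d | shift (points) |
|---|---|---|
| 1 | 5 | 5/30 = 0.17 |
| 3 | 5 | 15/30 = 0.50 |
| 3 | 10 | 30/30 = 1.00 |

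At an assumed SD of 6-10 points, the extremes are 0.17/10 = 0.02 SD and 1.00/6 = 0.17 SD.

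**Cross-check by simulation.** This used 40,000 replicates, 30 per arm and a true effect of 0, removing the 1-3 ILA patients with the worst perceived progress. If perceived progress predicts outcome perfectly (r = 1), the bias is +0.07 to +0.19 SD. At r = 0.7 it is +0.05 to +0.13 SD, and at r = 0.4 it is +0.03 to +0.08 SD. Removing the worst 1-3 from both arms gives about 0.00.

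**Against the pilot's imprecision.** The 95% CI half-width for a difference between arms, in SD units, is:
- ignoring clustering: 1.96 x sqrt(2/30) = 0.51;
- 8 clusters of 7.5, assumed ICC 0.05, 6 df: design effect 1 + 6.5 x 0.05 = 1.325; 2.447 x sqrt(2/30 x 1.325) = 0.73;
- 6 clusters of 10, assumed ICC 0.05, 4 df: design effect 1 + 9 x 0.05 = 1.45; 2.776 x sqrt(2/30 x 1.45) = 0.86.

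Allowing for clustering, the shift is about 2% (0.017/0.86) to 23% (0.167/0.73) of the half-width.

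**Retention.** Each withdrawal before week 4, in either arm and by any route, lowers 4-week completion by 1/60 = 1.7 percentage points.

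**The case against.** The strongest reply is that this is a descriptive pilot with no stated hypothesis. The synopsis plans within-group change scores, and the between-arm effect size serves one of several secondary objectives. Poor-progress withdrawal is discretionary, needs discussion with the Chief Investigator and is logged as an adverse event, so planners can see how often it happened. Therapists may use clinical judgement in any session and need not withdraw a patient in order to adapt treatment. The asymmetry partly reflects a safety provision, because a control patient has no other regimen to return to. Judging someone a poor responder takes time, so some withdrawals will fall after week 4 and leave the primary outcome untouched.

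All of that stands, and it limits the weight of the point. It does not remove it: logging withdrawals shows their number but does not recover the outcomes.

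Three stronger readings are tempting, and the documents do not support them.

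- **That the deterioration rules bias the comparison.** Sections 4.14 and 4.5.3.4 apply in both arms. They lose outcomes, but nothing suggests an imbalance in number or severity.
- **That within-group change is inflated.** The week 2, 4 and 6 measures run only up to discharge. Patients discharged early may be the better ones, so the net direction is unknown.
- **That Phase III would be undersized by a known amount.** Required size varies as 1/difference squared. An assumed true difference of 3 points overstated by 0.17-1.00 would cut it by 1 - (3/3.17)^2 = 10% to 1 - (3/4)^2 = 44%. This needs planners to take the pilot point estimate at face value, whereas 4.16 promises confidence intervals. The 3 points are also an assumption.

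**Conclusion.** The point holds for the 7.1.1 poor-progress route, as prompted by the training in 4.10. Followed as written, it can shift the between-arm 4-week mRMI estimate towards ILA, and likewise Fugl Meyer and SwePASS. Three conditions are needed: withdrawal before week 4, worse outcomes in those withdrawn than in those retained, and no later measurement. The first two cannot be checked from the documents; the third is the natural reading of the available text, subject to the two unreadable diagrams.

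The illustrated size is modest and well inside the pilot's random error. The case for acting is that the error is systematic, has a known direction under those conditions, and is cheap to prevent. Withdrawal is not needed to protect the patient, since 4.9 already leaves delivery of the ILA to the treating team. A patient who has gone back to standard care is still in rehabilitation and can usually be assessed.

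For 4.14 and 4.5.3.4 the conclusion is narrower: lost outcomes and lower retention, with no between-arm shift if balanced. The change should be made, but the flaw does not undermine the pilot.

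**What to change.** - **7.1.1 (poor-progress and non-compliance routes) and 4.10:** replace withdrawal from the study with discontinuation of the trial treatment. Continue the assessments already scheduled in 4.12 unless the participant declines or shows unwillingness.
- **4.14:** do the same where assessment is clinically appropriate and the participant is willing. Otherwise record vital status and the already scheduled 3-month modified Rankin Scale, where permitted. These do not replace a missing 4-week mRMI.
- **4.5.3.4:** leave the safeguards for people who have lost capacity as they are. They make staying in the study depend on clinical appropriateness, and changing them needs ethics review.
- **4.16:** state that participants are analysed in their cluster's allocated arm. Report treatment discontinuation, with its reason, separately from missed assessments, by arm, next to 4-week retention.

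The cost is a protocol amendment, any matching change to the participant information, and a few extra assessments, some in sicker patients. No new measure or time point is needed, apart from recording vital status where assessment is not possible.
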